5.1 Imputation rules

Table 5-1 Imputation of start dates (AE, CM) and assessments (LB, EG, VS, PRO)

Missing Element	Rule
day, month, and year	
 No imputation will be done for completely missing dates
day, month	
 If available year = year of study treatment start date then 
 If stop date contains a full date and stop date is earlier than study treatment start date then set start date = 01JanYYYY Else set start date = study treatment start date. If available year >year of study treatment start date then 01JanYYYY If available year <year of study treatment start date then 01JulYYYY
day	
 If available month and year = month and year of study treatment start date then 
 If stop date contains a full date and stop date is earlier than study treatment start date then set start date= 01MONYYYY. Else set start date = study treatment start date. If available month and year >month and year of study treatment start date then 01MONYYYY If available month and year <month year of study treatment start date then 15MONYYYY

AE: Adverse Events; CM: Concomitant Medications; LB: Laboratory; EG: ECG; VS: Vital Signs; PRO: Patient Report Outcomes

Table 5-2 Imputation of end dates (AE, CM)

Missing Element	Rule (*=last treatment date plus 30 days not >(death date, cut-off date, withdrawal of consent date))
day, month, and year	
 Completely missing end dates (incl. ongoing events) will be imputed by the end date of the on-treatment period*
day, month	
 If partial end date contains year only, set end date = earliest of 31DecYYYY or end date of the on-treatment period *
day	
 If partial end date contains month and year, set end date = earliest of last day of the month or end date of the on-treatment period*

Imputation of start and end dates will be used in analysis sets to derivation purposes. Any event with partial/missing dates will be displayed as such in the data listings. Any event which are continuing as per LPLV or cut-off date will be shown as 'ongoing', rather than an imputed end date provided, and duration and outcome will be kept in blank. Any event with missing end date will be shown as blank, and duration and outcome will be kept as blank, except for "not recovered/not resolved", "recovering/resolving" and "unknown" outcomes.

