$PDI \text{ (dosing unit / unit of time)} = \text{Planned cumulative dose (dosing unit)} / \text{Duration of exposure (unit of time)}$.

Note that eltrombopag is administered with a tapering regime. Therefore, for some patients, the duration of exposure will not include the time after tapering when they are not getting any dose. The **planned dose** is the starting dose of treatment which was defined for the patient by protocol.

Relative dose intensity (RDI) is defined as follows:

RDI = DI (*dosing unit / unit of time*) / PDI (*dosing unit / unit of time*).

e.g. RDI = DI (92.7 mg/day) / PDI (100 mg/day) = 0.927

Study day

The study day for efficacy (platelet counts) and safety assessments (e.g. adverse event onset, laboratory abnormality occurrence, vital sign measurement, dose interruption etc.) will be calculated as the difference between the date of the event (onset date of an event, assessment date etc.) and the start of study treatment plus 1. The first day of study treatment is therefore study day 1. Example: if start of study treatment is on 05-Jan-2014 and start date of an adverse event is on 09-Jan-2014 then the study day of the adverse event onset is 5. For safety assessments before start of study treatment, the study day is negative and derived by (date of event – start date of study treatment). For example: if start of study treatment is on 05-Jan-2014 and date of lab measurement is on 02-Jan-2014 then the study day of the laboratory abnormality is -3. Note, the day of start of study treatment is day 1, and the day before the date of first study treatment is day – 1, not day 0.

Baseline

The **baseline** is the result of an investigation describing the “true” state of the patient before start of eltrombopag.

The last available assessment on or before the date of start of eltrombopag is taken as “baseline” assessment. In case, assessment is captured pre-dose on first day of eltrombopag (e.g. PROs), this assessment is used for baseline.

On-treatment assessments and observation periods

The overall observation period will be divided into three mutually exclusive segments:

1. **pre-treatment period:** from day of patient’s informed consent to the day before first dose of eltrombopag

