Time windows for multiple assessments

In order to summarize data of assessments collected over time (including any unscheduled visits), the assessments will be time slotted. If more than one assessment is done within the same time window, the assessment performed closest to the target date will be used. If 2 assessments within a time window are equidistant from the target date, then the earlier of the 2 assessments will be used. If multiple assessments on the same date then the worst case will be used. The end of treatment assessment will be included if collected within 30 days of the last treatment date. Data from all assessments (scheduled and unscheduled), including multiple assessments, will be listed.

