2.5.3 Handling of missing values/censoring/discontinuations

No imputation will be used for missing platelet values.

After achieving CR, at least two platelet counts should be available (at least 14 days apart) to assess maintenance around $100 \times 10^9 / L$ for two months and to assess sustained response off treatment after tapering (if tapering ends prior to month 11).

A patient who discontinues early from the study (before month 12, e.g. withdrawal of consent) will not be considered for sustained response off treatment.

See mapping of visits in Section 2.1.1 (Time windows).

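### SAP Table 5-1 re-dates partly dated lab, ECG, vital-sign and PRO measurements to the first dose, where an on-treatment value can become the baseline

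*SAP*

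**What the plan says.** SAP 5.1, Table 5-1, is titled "Imputation of start dates (AE, CM) and assessments (LB, EG, VS, PRO"). One set of rules therefore covers adverse-event and medication start dates and the dates of laboratory, ECG, vital-sign and patient-reported-outcome (PRO) assessments.

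- **Partial date matching the first-dose month (day missing) or first-dose year (day and month missing).** One exception applies when a complete stop date precedes first dose. Otherwise: "Else set start date = study treatment start date".
- **Day missing, later month.** "If available month and year >month and year of study treatment start date then 01MONYYYY".
- **Nothing known.** "No imputation will be done for completely missing dates".
- **Use.** The text after Table 5-2 says "Imputation of start and end dates will be used in analysis sets to derivation purposes".

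SAP 2.1.1 defines baseline as follows: "The last available assessment on or before the date of start of eltrombopag is taken as" baseline. It adds that an assessment taken pre-dose on the first day is the one used. Separately, under the heading on time windows for multiple assessments, it says "If multiple assessments on the same date then the worst case will be used". Nothing in the SAP excludes a record with an imputed date from serving as baseline.

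**The concern.** For an adverse event, defaulting to the first-dose date is cautious, because the event falls in the on-treatment period and counts as treatment-emergent. For a measurement the same default does something different. It moves a value observed on treatment to the one date on which a record can still qualify as baseline.

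Baseline feeds change from baseline for platelets and PROs, the laboratory shift tables and worst post-baseline grades (SAP 2.8.3), and the ECG and vital-sign criteria defined as change from baseline (SAP 2.8.4.1 and 2.8.4.2). If an on-treatment value takes the baseline slot, the reference is wrong for that patient and parameter, and the value no longer stands among the post-baseline data.

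**Working it through.** The plan states no figure on this point, so there is none to reproduce. The check applies the written rules to dates and then to assumed values.

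**Inputs.** Table 5-1 without a stop date; the baseline and same-day rules of SAP 2.1.1; the SAP's own example first-dose date, 05-Jan-2014 (2.1.1, study day); haematology on Day 1 and then weekly for 8 weeks (protocol 8.3.1); liver tests before initiation and then every 2 weeks during dose adjustment (protocol 6.5.2); an ECG planned at screening only (protocol 8.4.3). All measured values below are illustrative assumptions.

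**Step 1: where partly dated visits go.**

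| Study day | True date | Day missing | Day and month missing |
|---|---|---|---|
| 8 | 12-Jan-2014 | 05-Jan (Day 1) | 05-Jan (Day 1) |
| 15 | 19-Jan-2014 | 05-Jan (Day 1) | 05-Jan (Day 1) |
| 22 | 26-Jan-2014 | 05-Jan (Day 1) | 05-Jan (Day 1) |
| 29 | 02-Feb-2014 | 01-Feb (Day 28) | 05-Jan (Day 1) |
| 183 | 06-Jul-2014 | 01-Jul (Day 178) | 05-Jan (Day 1) |

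With only the day missing, the problem is confined to the first-dose month. With the month also missing, it extends over the first-dose year.

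**Step 2: which visits can be affected.** A visit s days after first dose leaves the first-dose month if first dose was in the last s days of that month. Over 365 equally likely first-dose days, the share staying in the month is (365 − 12s)/365:

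- Day 8 (s = 7): 281/365 = 77%
- Day 15 (s = 14): 197/365 = 54%
- Day 22 (s = 21): 113/365 = 31%
- Day 29 (s = 28): 29/365 = 8%

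The mean number of post-dose visits in the start month, assuming a 30-day month and an evenly spread start day d, is:

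- weekly haematology: mean of floor((30 − d)/7) = 50/30 = 1.67
- two-weekly liver tests: mean of floor((30 − d)/14) = 18/30 = 0.6
- PROs (every 3 months) and ECG (screening only): no scheduled post-dose assessment in the start month

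These figures count visits that the rule would reach if the day were missing. They do not count records with a missing day.

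**Step 3: which value becomes baseline.** The last column applies the worst-case rule to baseline.

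| Case | Screening | True Day 1 | Moved value | Baseline |
|---|---|---|---|---|
| Platelets, no Day 1 record | 15 | none | 90 | 90 (moved) |
| ALT, no Day 1 record | 25 | none | 120 | 120 (moved) |
| ALT, moved value worse | 25 | 30 | 120 | 120 (moved) |
| ALT, moved value better | 25 | 30 | 20 | 30 (true Day 1) |
| Platelets, moved value better | 15 | 20 | 90 | 20 (true Day 1) |

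The first two rows need only the baseline definition. The third also needs the worst-case rule to be carried over to baseline. If the pre-dose sentence governs and the Day 1 sample was pre-dose, the third row gives 30.

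**Step 4: direction.** Take a patient with no Day 1 chemistry.

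- Screening ALT 0.8 × ULN and a moved on-treatment value of 4 × ULN: baseline becomes 4 × ULN. No upward shift from that value is shown, and it leaves the post-baseline count above 3 × ULN.
- Screening ALT at the eligibility limit of 3.0 × ULN (protocol 5.2, criterion 10) and a moved on-treatment value of 0.8 × ULN: baseline becomes 0.8 × ULN. A later return to 3.0 × ULN appears as a new rise.

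The distortion can therefore hide a change or create one.

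**The case against.** Much of the opposing case stands.

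- **A reader might infer that the rules always turn a moved value into the baseline.** They do not. The same-day worst-case rule is written for time-slotted summaries, not in the baseline definition, and that definition says a pre-dose Day 1 assessment is used. For platelets, a Day 1 count is scheduled and will usually be the lower one, so it would normally remain baseline. What survives is the case with no Day 1 record, and an unresolved question of which sentence governs when there is one. Whether chemistry is scheduled on Day 1 cannot be read from the public copy of protocol Table 8-1.
- **A reader might infer a one-way safety bias that conceals liver signals.** Step 4 shows both directions. Protocol Table 6-4 also calls for repeat liver tests after an ALT or AST above 3 × ULN; fully dated repeats would stay post-baseline, and all laboratory data are listed.
- **A reader might extend the point to the primary endpoint**, because SAP 2.5.3 asks that "at least two platelet counts should be available (at least 14 days apart") and a date moved to the 1st of a month could widen a gap. SAP 2.5.1 uses only scheduled visits for platelets in the first 12 months, and both sections refer to visit mapping. Counts are weekly and then two-weekly, so two months normally contain several pairs at least 14 days apart. An imputed date would matter only if nearly all other counts were missing.
- **Partial dates should be rare.** Missing values are queried before lock (protocol 11.2), and data for primary variables are fully source-verified (protocol 11.3). This limits how often the rule is triggered; it does not correct what the rule does.

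**Conclusion.** The point holds as a limited defect in a derivation rule. Read literally, Table 5-1 dates a partly dated on-treatment measurement to the first dose, and SAP 2.1.1 then lets it serve as baseline. This happens when no true Day 1 record exists. It also happens when the moved value is the worse same-day value, but only if the worst-case rule is taken to apply to baseline, which the SAP leaves open.

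The effect is on individual patients' change from baseline, shifts and worst post-baseline categories, in either direction. Its size cannot be computed, because the documents do not say how many assessment dates are partial; the number is probably very small. The documents give no support for a threat to the primary result or for a systematic safety bias. Priority is low, and the reason to act is that the correction is simple.

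**What to change.** 1. Limit Table 5-1 to adverse-event and concomitant-medication start dates.
2. Assign a partly dated scheduled assessment to its nominal visit, using the visit label in protocol Table 8-1.
3. State that no assessment with an imputed date may serve as baseline, and that a pre-dose Day 1 value takes priority over any other same-day value.
4. Keep partly dated unscheduled assessments known to be after first dose in the worst post-baseline summaries, and exclude them from baseline and by-visit summaries. Removing them from every derivation would conflict with SAP 2.8.3, which includes all available laboratory assessments up to 30 days after last dose, and could discard abnormal results.

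The cost is one table title and a few sentences. A few partly dated values leave the by-visit summaries. SAP section 1 says the primary CSR is already final, so any small differences in the final CSR may need a footnote.

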2.4.2 Rescue therapy

Any ITP-directed medication or therapy, other than eltrombopag, given during the trial with the aim to increase platelet count for the patients who have clinically significant bleeding will be considered a rescue therapy and must be recorded on the appropriate CRF page (Form: Concomitant Medication, the category value at the form: Rescue medication). A patient who receives rescue medication or therapy between Step 2 and Step 3 will not be eligible for Step 3. A patient who receives rescue medication or therapy between Step 3 and Step 4 will not be eligible for Step 4. A patient who receives rescue medication or therapy will not be considered in having achieved sustained response off treatment for the primary endpoint, unless the patient uses steroids ± IVIG as described below in the first 14 days of start of eltrombopag.

Steroids ± IVIG use as rescue medication:

In case of clinical need such as very low platelet count (<10×10⁹/L) and/or significant bleeding, treatment with steroids ± IVIG and platelet transfusion is permitted together with eltrombopag for the first 14 days, calculated from the first dose day of eltrombopag. Any rescue therapy started before Day 14 may be used after Day 14 if the dose is considered low dose as per protocol definition and is being tapered down (i.e., successively lower doses after day 14).

Rescue medication will be taken from the SDTM cm.sas7bdat dataset where cmcat='RESCUE MED' for rescue therapy and exported as an EXCEL file. The clinical team will review the records captured in an Excel spreadsheet. Medications which were not considered as rescue therapy were flagged as 'Y' for the column 'NOT_RESCUE'. Per protocol, medications prior to Day 14 are not considered as rescue medication in the efficacy derivations and will be programmatically excluded. Medications that started prior to Day 14 and were still being tapered after Day 14 will also be programmatically excluded from efficacy derivations.

Once the database has locked the data will be rechecked again for any changes or new data that needs flagging.

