2.8.4.4 Bleeding adverse events used in efficacy analyses

All Adverse event (AEs) will be taken from the ae.sas dataset and exported as an Excel file. The clinical team will review the records captured in an Excel spreadsheet and mark with a 'Y' in new variable 'bleed_flag', those terms which are considered as bleeding AEs. Bleeding events on or before Day 7 are not considered in the efficacy derivations and will be programmatically excluded.

Once the database has locked the data will be rechecked again for any changes or new data that needs flagging.

The spreadsheet will contain three (3) tabs, the first tab is the final tab used in the analysis. The second and third tabs are used by the clinical team to flag the bleeding records and provide comments.

The first tab contains the following variables: reported term for the adverse event (AETERM), dictionary-derived term (AEDECOD), bleeding flag(Bleed_flag), the second tab contain the same variables with clinical team comments. Third tab contain additional variables to document decision making: unique subject identifier (USUBJID), reported term for the adverse event (AETERM), dictionary-derived term (AEDECOD, AEDECOD = 'Thrombocytopenia') and comments.

The spreadsheet will be imported into the programming environment (GPS) and merged with the patient data for the analysis where bleeding events will be filtered by the value 'Y' for the variable 'Bleed_flag' using the first tab. The EXCEL document will be stored in CREDI in the study folder ETB115J2411/Administrative Files (study level)/RAP or RAMP Meeting and in GPS in the study folder CETB115J\CETB115J2411\csr_1\util for primary CSR and folder CETB115J\CETB115J2411\csr_2\util for final CSR.

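### The SAP's partial-date rule can move a late rescue or bleeding record into the early window that efficacy ignores, and no efficacy-specific rule counters it

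*SAP*

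**What the plan says.** SAP 5.1, Table 5-1, covers start dates of adverse events (AE) and concomitant medications (CM).

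- **Year only, equal to the treatment-start year; or month and year known and equal to the treatment-start month:** "Else set start date = study treatment start date". The one exception is a full stop date before treatment start. A late stop date does not prevent the move to Day 1.
- **Year only, later year:** "If available year >year of study treatment start date then 01JanYYYY".
- **Day missing, later month:** "If available month and year >month and year of study treatment start date then 01MONYYYY".
- **Nothing known:** "No imputation will be done for completely missing dates".

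The text after the tables adds: "Imputation of start and end dates will be used in analysis sets to derivation purposes". Efficacy is not excepted.

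Two efficacy sections then discard early records. SAP 2.4.2 states: "Per protocol, medications prior to Day 14 are not considered as rescue medication in the efficacy derivations and will be programmatically excluded", and also: "Medications that started prior to Day 14 and were still being tapered after Day 14 will also be programmatically excluded from efficacy derivations". SAP 2.8.4.4 states: "Bleeding events on or before Day 7 are not considered in the efficacy derivations and will be programmatically excluded". SAP section 4 gives the bleeding exclusion a narrower scope, secondary endpoints 3, 4 and 6. Under SAP 2.5.2, new rescue medication after Day 14 bars Step 4 whenever it occurs up to Month 12.

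**The concern.** Placing an incompletely dated event on the first day of treatment is cautious for safety, because the event is then counted as treatment-emergent. For efficacy it can work the other way, because Day 1 lies inside both windows that the derivations ignore. A rescue course or bleed that truly came later, and should fail the patient, can then leave the derivation.

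The planned clinical review does not clearly repair this. The NOT_RESCUE flag only removes records from rescue status. The bleeding tab used in the analysis holds the reported term, the coded term and a flag, but no date.

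The direction also differs from the plan's other conventions. Protocol 12.4.3 does not count patients with missing platelet assessments as remissions, and SAP 2.1.1 takes the worst case when several assessments share a date. In a single-arm trial decided by a responder count, a few hidden failures matter if the count is near the cut-off.

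**Working it through.** **1. The plan's own rule.** Inputs from SAP 3.1.2: N = 105, P0 = 0.15, P1 = 0.25, reject at 23 or more. For X ~ Bin(105, p), P(X >= 23) is 0.0373 at p = 0.15 (stated 0.037) and 0.7995 at p = 0.25 (stated 0.800; the rounding difference has no bearing here). For N = 101 and cut-off 22, the results are 0.0433 and 0.8042 (stated 0.043 and 0.804).

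**2. How often a late event is moved early.** The documents give no count of partial dates, so this step rests on an assumption: treatment starts uniform over a calendar year and true event days uniform over the range shown. Table 5-1 was applied to every combination.

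| Known part of date | True day | Set to Day 1 | Lands on Day 14 or earlier | Lands on Day 7 or earlier |
|---|---|---|---|---|
| Year only | 15-365 | 48% | 52% | 50% |
| Month and year | 15-365 | 1.3% | 4.2% | 2.5% |
| Month and year | 15-31 | 28% | 70% | 47% |
| Year only | 8-365 | 49% | 53% | 51% |
| Month and year | 8-365 | 2.6% | 6.1% | 4.1% |
| Year only | 120-365 | 34% | 37% | 35% |
| Month and year | 120-365 | 0% | 0% | 0% |

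Hand check of the first row: an event on Day d shares the start year with probability (366 - d)/365. Over d = 15 to 365 the mean is 176/365 = 0.482. Starts on 19-31 December put 1 January on Day 14 or earlier, which adds 13/365 = 0.036, giving 0.518. Reading the rescue window strictly as before Day 14 gives 0.482 + 12/365 = 0.515 for year-only records, and 67% instead of 70% for month-and-year records on Days 15-31.

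**3. Which records matter for which endpoint.**
- *Rescue, primary endpoint.* Any new course after Day 14 is a failure, so the Day 14 column applies. The exposed records are year-only ones in the start year (or with 1 January falling in the window) and day-missing ones in the start month or early in the next month.
- *Bleeding, primary endpoint.* Bleeding counts only during taper and afterwards. A start-month bleed is at latest Day 31 and a next-month bleed at latest Day 62. If complete response is first recorded at the Week 2 visit (about Day 8), two months of maintenance (2 x 30.44 = 61 days) put taper at about Day 68 or later. Those bleeds could not have failed the patient on their true dates, so moving them changes nothing. The move to Day 1 therefore matters only for year-only records, because Day 1 precedes taper. If bleeds in or after taper are taken as Days 120-365, 34% of year-only records go to Day 1. Separately from the early windows, a day-missing bleed in the month when taper begins goes to the 1st of that month, which can also precede taper.
- *Bleeding, secondary endpoints 3, 4 and 6.* The Day 7 column for true Days 8-365 applies: 51% of year-only and 4.1% of day-missing records.

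**4. The opposite direction.** With true days uniform over 366-730, about 50% of year-only records are imputed to within the first 365 days. For true Days 366-396, about 48% of day-missing records are. Such a rescue record would count as a false failure of the primary endpoint.

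**5. Consequence for the test.** At P0 = 0.15 and N = 105, 22 responders (21.0%) give p = 0.063 and 23 (21.9%) give p = 0.037. If the true rate is 15% and the rule adds on average k false responders, the chance of rejecting is P(X >= 23) with p = 0.15 + k/105:

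| k | 0 | 0.5 | 1 | 2 | 3 |
|---|---|---|---|---|---|
| P(reject) | 0.037 | 0.051 | 0.067 | 0.110 | 0.169 |

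**The case against.** The best reply is that such records should be rare. Visits are weekly and then every two weeks, with bleeding assessed at each (Protocol 8.3). Adverse-event start and end dates are to be recorded (10.1.1), missing values are queried (11.2), and data for primary variables are fully source-verified (11.3). A year-only date for an on-study rescue course is hard to picture, and rescue is probably concentrated early, so uniform event days may overstate the effect. This stands: the percentages describe how the rule acts on a record once it exists, not how many exist.

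Forgiveness of rescue is also conditional. A dose increase after Day 14 still fails Step 4, and use continuing past Day 14 is accepted only if low-dose and tapering. A record set to Day 1 with a stop date months later is therefore not clearly excluded. This stands too.

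A reader might go further and infer that undated failures become responders, or that the bias runs only towards success. The documents support neither. Wholly missing dates are not imputed; the gap there is that their efficacy handling is unstated. Most day-missing records in later months stay outside the windows. Events after Month 12 can be pulled back against response. A patient counts as a responder only if every other step is met, and a platelet count below 30 x 10^9/L during or after taper still fails the patient.

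What remains is that the written rule, followed as it stands, can discard a true failure, and nothing in the SAP prevents it.

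**Conclusion.** The point holds as a gap in how partial dates are handled for efficacy. The exposure is clearest for rescue medication. For bleeding it is confined to year-only records as far as the first-dose imputation and the primary endpoint are concerned, and to records moved into Days 1-7 for secondary endpoints 3, 4 and 6.

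The shares rest on uniform start and event dates. The number of affected records is unknown and may be zero. The step from 22 to 23 responders shows how finely the test is balanced at its cut-off; it does not measure what this rule did. A reader might infer that the reported primary result is unsafe, but nothing in the documents shows that any record was affected. The matter should be settled by a count and a sensitivity analysis in the final CSR.

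**What to change.** In SAP 5.1:

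- Keep Table 5-1 for treatment-emergent classification.
- For rescue medication, platelet transfusions and bleeding AEs used in efficacy, set a partial start date to the latest date consistent with its known parts, the stop date and, for the primary endpoint, the Month 12 window. Name the transfusions taken from the procedures dataset (ADPR, SAP 2.4.2) explicitly, because Table 5-1 lists only AE and CM start dates.
- State how wholly missing dates are handled in the efficacy derivations.
- Reconcile SAP 2.8.4.4 with SAP section 4 on whether the Day 7 bleeding exclusion reaches the primary endpoint.
- List every rescue, transfusion and bleeding record with a partial or missing start date.
- Because the primary CSR is final, leave the reported primary analysis in place and give the primary endpoint under both date rules as a sensitivity analysis in the final CSR.

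The cost is a few sentences, one query and a small programming change. The drawback is that some patients with permitted early steroid use but a missing day will be scored as failures in the sensitivity analysis whenever the latest compatible date falls after Day 14. The listing lets a reader see how many. If it is empty, the matter is closed.
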